### 5.3 Study Size, Duration and Location

The study will enroll approximately 12 subjects up to a maximum of 15 subjects to account for potential study withdrawals, discontinuations or unconfirmed diagnosis of NPC. It is anticipated that this study will take four years to complete, with approximately four subjects to be enrolled per year.

Study-related assessments will be conducted at St. Louis Children's Hospital.

For each subject, the first phase of the protocol will be conducted over seven weeks; one-week inpatient followed by five weeks outpatient administrations with a post-dose safety evaluation performed one week after the final dose. The second phase of the protocol will be an open label extension conducted in an out-patient setting over six months with a post-dose safety evaluation performed one week after the final dose.

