#### **5.6 Dosing and Dose Adjustments**

Adrabetadex will be administered intravenously to specifically target liver disease. In the first phase of the study, dosing frequency will be twice a week with IV adrabetadex for six weeks for a total of 12 administrations. Subjects will be evaluated at each study visit for evidence of adverse effects.

Adrabetadex is provided as a 200 mg/mL solution and infused at this concentration and will be administered at a rate of 250 mg/kg/hr. A 5 kg infant receiving a 500 mg/kg dose, for example, will receive 12.5 ml of the 200 mg/ml solution.

Doses to be studied are 500 and 1000 mg/kg.

Six subjects will be studied at each dose level

Cohort 1	Subjects 1-6	500 mg/kg
Cohort 2	Subjects 7-12	1000 mg/kg

The DSMC will review data from the first phase of the study for all six subjects in Cohort 1 prior to initiation of Cohort 2.

Subjects who do not tolerate (section 7.9) the initial 500 mg/kg dose may have the dose decreased to 250 mg/kg/dose and remain at this dose for the remainder of the study.

Subjects who do not tolerate the 250 mg/kg dose will be withdrawn from the study.

Subjects who do not tolerate the first two doses of 1000 mg/kg dose may have the dose decreased to 500 mg/kg and remain at this dose level for the remainder of the study.

Subjects may be withdrawn for any Grade 3 AE (per NCI's CTCAE) possibly, probably or definitely related to study drug; any Grade 4 toxicity; any subject with pulmonary complications or evidence of renal injury; or determination that the limit of safety and/or tolerability has been reached. In the context of adrabetadex administration, limit of tolerability is defined as a sustained increased respiratory rate over 30 minutes or decreased SaO2 (<90%) resulting in need for, or increase in sustained need for supplemental oxygen, or evidence of renal injury as defined as a serum creatinine (SCr) rise > 0.5 mg/dl.

Subjects who demonstrate significant reduction either in the glycine-conjugated trihydroxycholanic acid biomarker or serum bilirubin (direct bilirubin or direct bilirubin:total bilirubin ratio) will be allowed to crossover into the second phase of the study, an open-label phase of six months duration. In this phase of the study, dosing frequency will be monthly with IV adrabetadex for six months for a total of six administrations. Subjects will be evaluated at each study visit for evidence of adverse effects.

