### **6.6.1 Hematology/Chemistry**

Blood samples for the clinical laboratory tests will be collected by a qualified person using either the central line, by indwelling catheter, or by venipuncture.

Testing will include the following (phase 1: 2.5 mls/time point; 10 mls total over six weeks, phase 2: 2.5 mls/time point; 10 mls total over six months):

Hematology: complete blood count (CBC) with differential and platelet count, and prothrombin time (PT).

Clinical chemistry: electrolytes, glucose, blood urea nitrogen (BUN), creatinine, AST, ALT, GGT, alkaline phosphatase, bilirubin (direct and total), albumin, calcium, magnesium, phosphorus, and CK.

In phase 1, testing will occur at baseline, 2, 4 and 6 weeks. In phase 2, testing will occur at baseline, 2, 4, and 6 months. For study subjects, the amount drawn will not exceed the lesser of 50 ml or 3 ml per kg in an 8 week period and collection may not occur more frequently than 2 times per week.

Lab results do not need to be resulted and reported prior to dosing.

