### **8.3 Phlebotomy**

Phlebotomy is a risk/discomfort of this study. An anesthetic cream such as EMLA is an option to reduce discomfort. Infection and bruising are possible at the site of the blood draw. At each time point the maximum blood draw is 6 mL. In Phase 1, the maximum blood draw over 6 weeks is 24mL. In Phase 2, the maximum blood draw over 6 months will be 24mL. Nursing staff will monitor blood-drawing volumes. If blood limits are an issue, testing will be prioritized by the investigators. Safety laboratory tests will take priority over investigational testing. Not obtaining a test due to blood limit prioritization will not be considered a protocol deviation.

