## **9.9 Phase 2: Open-Label extension (Doses 13-18)**

Subjects who demonstrate significant reduction either in the glycine-conjugated trihydroxycholanic acid biomarker or serum bilirubin (direct bilirubin or direct bilirubin:total bilirubin ratio) will be allowed to crossover into the second phase of the study, an open-label phase of six months duration. In this phase of the study, dosing frequency will be monthly with IV adrabetadex for six months for a total of six administrations. Subjects will be evaluated at each study visit for evidence of adverse effects.

Entry into the open-label extension phase will occur after completion of phase 1 final evaluation. Doses 13-18 may be administered as an outpatient. In the extension phase, the subjects will continue at the same dose (mg/kg) as they received for the 12th adrabetadex infusion.

Because the adrabetadex drug will be infused through peripheral IV access for doses 13-18, the 200 mg/mL solution will be diluted 4-fold into sterile saline prior to infusion. A 5 kg infant receiving a 500 mg/kg dose, for example, will receive 50 ml of the diluted adrabetadex (50 mg/ml solution).

IV adrabetadex will be administered via peripheral IV access at a rate of 250 mg/kg/hr. Rate may be decreased in 25 mg/kg/hr increments to 175 mg/kg/hr if required. The rate and reason for reduction will be recorded.

Vital signs (temperature, heart rate, respiratory rate, supine blood pressure, and  $\text{SaO}_2$ ) and standard neurological checks will be conducted at least every 30 minutes during and then for the two hours after drug administration. Subject may be discharged 2 hours post administration if no issues.

If there is evidence of clinical deterioration during the open label phase (based on assessment by the patient's physician), dosing frequency may be increased. Increasing dosing frequency more frequently than monthly will necessitate reinsertion of a PICC line (see Section 8.8).

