## **9.10 Phase 2: Post-dose Safety Evaluation**

Subject will be evaluated by history  $7 \pm 2$  days after the 18th adrabetadex infusion. History will be taken in person or by telephone by the study coordinator and consist of an interim medical history. The study coordinator will document the conversation and history. If discharged to home then study team will follow-up by phone on a weekly basis for two additional weeks.

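### Section 9.9 allows Phase 2 dosing above monthly while creatinine stays at baseline, 2, 4 and 6 months, so more infusions can pass between renal checks than in Phase 1

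*Combined protocol and SAP*

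**What the plan says.** Section 9.9 plans Phase 2 so that "dosing frequency will be monthly with IV adrabetadex for six months for a total of six administrations". It then adds that, if the patient's physician judges that there is clinical deterioration, "dosing frequency may be increased". The stated consequence is that "Increasing dosing frequency more frequently than monthly will necessitate reinsertion of a PICC line". No upper frequency, revised dose total or added laboratory monitoring is given.

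Section 6.6.1 includes creatinine in the chemistry panel and fixes the timing: "In phase 2, testing will occur at baseline, 2, 4, and 6 months". The schedule does not depend on dosing frequency, and results need not be available before a dose is given. Urinalysis (6.6.2) has the same fixed Phase 2 time points. The outline of admissions and testing in section 9 mentions laboratory testing in months 2 to 6 but adds no creatinine time point.

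Section 5.6 includes in its limit of tolerability "evidence of renal injury as defined as a serum creatinine (SCr) rise > 0.5 mg/dl".

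On the closing safety check, 9.10 counts "days after the 18 th adrabetadex infusion", whereas 5.3 describes Phase 2 as "conducted in an out-patient setting over six months with a post-dose safety evaluation performed one week after the final dose".

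**The concern.** The renal rule in 5.6 can act only when creatinine is measured. In Phase 1, twice-weekly dosing is paired with fortnightly creatinine. Section 9.9 lets dosing intensify in Phase 2 without bringing any of that monitoring back.

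The kidney is a sensible organ to watch. Section 2.3.1.2 reports tubular changes after repeated IV dosing, only partly reversible in rats at 100 and 400 mg/kg; the trial doses are 500 and 1000 mg/kg. The infants concerned would already be deteriorating. They could receive more drug before a creatinine rise is sampled than Phase 1 allowed.

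A smaller matter sits beside this. If the last infusion is not dose 18, the closing check in 9.10 is timed from the wrong event or from one that never happens.

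**Working it through.** The plan gives no figure to reproduce. The check is a count of infusions between scheduled creatinine draws.

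**Inputs from the documents.** Phase 1: 12 infusions, with chemistry at baseline, 2, 4 and 6 weeks. Phase 2: six monthly infusions (doses 13 to 18), with chemistry at baseline, 2, 4 and 6 months.

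**Assumptions.** A month is 30.44 days, dose 13 is day 0, and blood is drawn before any infusion on the same day. Section 9.9 names no raised frequency, so I use every two weeks, weekly and twice weekly. The visit months can be read two ways:
- Reading A counts months from dose 13, with draws on days 0, 61, 122 and 183.
- Reading B follows the labels in the section 9 outline, where Month 1 is dose 13, with draws on days 0, 30, 91 and 152.

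**Reference values.** Phase 1: 12 infusions / 3 intervals = 4 per interval. Phase 2 at monthly dosing: at most 2 per interval under either reading.

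**Six administrations as a cap.** Largest number of infusions between consecutive draws, by the dose after which frequency rises:

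| Reading | Raised frequency | After 13 | After 14 | After 15 | After 16 | After 17 |
|---|---|---|---|---|---|---|
| A | every two weeks | 5 | 4 | 4 | 4 | 2 |
| A | weekly | 6 | 6 | 4 | 4 | 2 |
| A | twice weekly | 6 | 6 | 4 | 4 | 2 |
| B | every two weeks | 3 | 5 | 4 | 3 | 3 |
| B | weekly | 5 | 5 | 5 | 3 | 3 |
| B | twice weekly | 6 | 5 | 5 | 3 | 3 |

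Example (A, weekly, after dose 14): infusions on days 0, 30, 37, 44, 51 and 58 all precede the day-61 draw, which gives six.

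The maximum is 6, or 6/4 = 1.5 times Phase 1. Of the 30 cells, 18 are four or fewer and 5 reach six. From dose 16 onward no cell exceeds four.

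**No cap.** A two-month interval is 2 x 30.44 = 60.9 days:
- Every two weeks: 60.9 / 14 = 4.3
- Weekly: 60.9 / 7 = 8.7
- Twice weekly: 60.9 / 3.5 = 17.4

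**Is six a cap?** Once frequency rises, six months of dosing and six administrations cannot both hold. At weekly dosing from dose 13, dose 18 falls after 5 x 7 = 35 days. Section 9.9 does not say which gives way.

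**Closing check.** Sections 5.3 and 9.10 agree whenever dose 18 is the final dose. Under a cap that is true of every infant who completes Phase 2, at any frequency. They part only if an infant stops before dose 18, or if dosing goes past it and the 9.10 check then falls during treatment.

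**The case against.** The strongest reply is that the excess is small and rarely reached. The six-dose total, or doses 13 to 18, is repeated across the protocol and stands in the heading of 9.9. Nothing authorises a nineteenth infusion. Under that total most scenarios are no worse than Phase 1, and the worst adds two infusions. The infant must first respond, enter Phase 2, deteriorate and be escalated, in a trial of about 12 infants (maximum 15). Some deteriorating infants may be withdrawn under 7.7 instead. Other safeguards remain: adverse-event evaluation at each visit, vital signs at each infusion, withdrawal for renal injury, adverse-event reporting to 30 days after the last dose (11.6), and earlier committee review if circumstances call for it (11.4). Section 6.6.1 also leaves room for unscheduled blood tests.

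Most of this stands, and it limits the weight of the point. It does not remove it. None of those safeguards schedules a creatinine, vital signs would not show a creatinine rise, and withdrawal for renal injury as 5.6 defines it needs a measured value.

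Two stronger readings are tempting. A reader might infer that the plan allows 17 or 18 infusions between renal checks. That needs dosing past dose 18 at a twice-weekly rate, and the documents state neither. A reader might also infer that 5.3 and 9.10 contradict each other in general. They do not; they differ only for infants who stop early or are dosed past dose 18. The early-stopping case is not created by 9.9 either, since 9.8 counts from the 12th infusion in the same way.

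**Conclusion.** The gap is real but conditional, of minor to moderate weight. Followed as written, 9.9 and 6.6.1 let up to 6 infusions pass between creatinine draws against 4 in Phase 1, if six administrations is a cap and frequency rises early. Without a cap the count is about 4 to 5, 9, or 17 to 18, depending on the frequency chosen. At every two weeks the count therefore stays close to Phase 1; the gap becomes material at weekly or more often. These figures rest on assumed frequencies and on draws made as scheduled.

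This is a safety-monitoring matter. The documents give no ground for inferring harm to the Phase 1 primary endpoint, power or alpha. The 9.10 wording is an alignment only.

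**What to change.** **Changes**
- 6.6.1: while Phase 2 dosing is more frequent than monthly, draw safety chemistry including creatinine at least once every four infusions. Scheduled draws count toward this. It keeps the Phase 1 ratio.
- 9.9: state whether six administrations is a cap.
- 9.10: time the closing check from the last Phase 2 infusion, to agree with 5.3.

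**Cost under a cap.** Scheduled Phase 2 blood (6.6.1, 6.7, 6.8) is 4 x 2.5 + 4 x 0.5 + 0.5 + 4 x 1.75 + 0.5 = 20 ml. Six infusions in one interval need one extra draw: 20 + 2.5 = 22.5 ml. Section 8.3 states that "In Phase 2, the maximum blood draw over 6 months will be 24mL", so this fits.

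**Cost without a cap.** For one two-month interval, nine infusions at weekly dosing need two extra draws (20 + 5 = 25 ml), and 17 or 18 at twice weekly need four (20 + 10 = 30 ml). Both exceed 24 ml. Section 8.3 already puts safety tests ahead of research tests. Dropping all 10 ml of Phase 2 research blood leaves 24 - 10 = 14 ml, enough for five extra draws of 2.5 ml. Beyond that the 24 ml figure needs amending.

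**Eight-week limit.** Section 6.6.1 also caps blood at 3 ml/kg in 8 weeks, which is 15 ml at the protocol's example weight of 5 kg. With early escalation, late Phase 1 draws share that window. Week 6 (5.75 ml) + Phase 2 baseline (4.75 ml) + one extra draw (2.5 ml) = 13.0 ml, which fits. If week 4 (5.25 ml) also falls inside, the total is 18.25 ml, which does not. The existing schedule already strains the limit there: 5.25 + 5.75 + 4.75 = 15.75 ml with no extra draw. Research samples would be dropped first under 8.3, so the price is lost exploratory biomarker data in a few infants.

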## **9.10 Phase 2: Post-dose Safety Evaluation**

Subject will be evaluated by history  $7 \pm 2$  days after the 18th adrabetadex infusion. History will be taken in person or by telephone by the study coordinator and consist of an interim medical history. The study coordinator will document the conversation and history. If discharged to home then study team will follow-up by phone on a weekly basis for two additional weeks.

## **9.11 Adrabetadex dose**

The subjects will be enrolled in two cohorts.

Two dose levels will be evaluated. Dose levels for each cohort are:

Cohort 1	500 mg/kg
Cohort 2	1000 mg/kg

Subjects who do not tolerate the first dose of 500 mg/kg dose may have the dose decreased to 250 mg/kg dose. Subjects who do not tolerate 250 mg/kg dose will be withdrawn from the study. Subjects who do not tolerate the

first two doses of the 1000 mg/kg dose may have the dose decreased to 500 mg/kg. Decisions regarding tolerability will be made by the DSMC in conjunction with the investigators and local monitor.

If a subject withdraws from the protocol prior to the 12th drug infusion, they may be replaced.

These data from three subjects previously treated with IV adrabetadex support the utility of this plasma NPC biomarker as a potential outcome measure to monitor the effects of IV adrabetadex on peripheral tissues. Utilizing this data, we would have approximately 80% power to detect a 33% reduction in the plasma biomarker concentration in 5 subjects. Utilizing this data, we would have approximately 57, 80 and 99% power to detect a 25, 33 and 50%, respectively, reduction in plasma biomarker concentration in 5 subjects.

The secondary outcome measure for this trial is the plasma AST and ALT levels.

For group comparisons, such as comparing mean values of primary outcome measurements, the statistical significance of differences in mean values will be determined by a two-tailed single-factor ANOVA or Student's t test. To perform correlations, such as for comparison of primary/secondary outcome data with NIH severity scale values or clinical assessments, data will be analyzed using Pearson and Spearman correlations, as appropriate. A p-value of 0.05 or less was considered significant. A Bonferroni posttest correction will be used to adjust for multiple comparisons (e.g., when analyzing the panel of secondary outcome measures).

## 11. Adverse Events, Protocol Deviations, and Data Safety Monitoring

### 11.1 Definitions

**Adverse event:** An adverse event (AE) means any untoward medical occurrence associated with the use of a drug in humans, whether or not considered drug related.

**Suspected adverse reaction:** This is defined as any AE for which there is a reasonable possibility that the drug caused the AE. For the purposes of IND safety reporting, “reasonable possibility” means there is evidence to suggest a causal relationship between the drug and the AE. Suspected adverse reaction implies a lesser degree of certainty about causality than adverse reaction, which means any AE caused by a drug.

**Life-Threatening AE or Life-Threatening Suspected Adverse Reaction:** An AE or suspected adverse reaction is considered “life-threatening” if, in the view of the Investigator/Sponsor, its occurrence places the subject at immediate risk of death. It does not include an AE or suspected adverse reaction that, had it occurred in a more severe form, might have caused death.

**Serious Adverse Event or Serious Suspected Adverse Reaction:** An AE or suspected adverse reaction is considered “serious” if, in the view of the Investigator/Sponsor, it results in any of the following outcomes:

1. Death
2. A life-threatening adverse event
3. Inpatient hospitalization or prolongation of hospitalization
4. A persistent or significant incapacity or substantial disruption of the ability to conduct normal life functions
5. A congenital anomaly/birth defect

**Unexpected AE or Unexpected Suspected Adverse Reaction:** An AE or suspected adverse reaction is considered “unexpected” if it is not listed in the protocol or consent or is not listed at the specificity or severity that has been observed.

### 11.2 Adverse Event Classification

**Relationship to Investigational Drug:** The following two classifications should be used when evaluating the relationship of AEs and serious adverse events (SAEs) to the investigational drug:

- **Unrelated:** No relationship between the experience and the administration of study drug; rather, related to other etiologies such as concomitant medications or subject’s clinical state. The reaction can be reasonably explained by the known characteristics of the subject’s clinical state or other modes of therapy administered to the subject.
- **Related:** A reaction that follows at least a plausible temporal sequence from administration of the study drug.

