## **7.8 Adverse event assessments**

Adverse events will be assessed using CTCAE version 5.0. Safety and tolerability of adrabetadex will be determined as presented in Table 1 except for respiratory and audiological complications.

Subjects will be withdrawn or dose decreased if they experience systemic (decreased blood pressure, heart rate, allergic rash, wheezing), respiratory (sustained increased respiratory rate over 30 minutes or decreased SaO2 (<90%)), or central nervous system (altered level of consciousness, seizures) symptoms during drug infusion or within 2 hours post-infusion. Subjects will be withdrawn or dose decreased if CXR demonstrates pulmonary infiltrates likely related to drug administration. If the etiology of pulmonary infiltrates is not known, they dose may be repeated and a subsequent CXR obtained. If the subsequent CXR demonstrates increased pulmonary infiltrates, subject will be withdrawn.

**Table 1. Decision Table for Evaluating the Safety and Tolerability of IV adrabetadex in Individual Subjects (respiratory and audiological excluded)**

	Safety Profile of Individual Patient	Safety Decisions*
A	No AEs and no SAEs or Any number of Common Terminology Criteria for Adverse Events (CTCAE) Grade 1 drug-related AEs; ≤ 1 CTCAE Grade 2 drug-related AE; or	Repeat the current dose
B	2 CTCAE Grade 2 drug-related AEs (or	Repeat the current dose, Study a lower dose (if applicable)
C	≥ 3 CTCAE Grade 2 drug-related AEs or ≥ 1 drug-related SAE	Study a lower dose, or withdraw the subject and Evaluate the risk/benefit profile for dose escalation of other subjects
D	Any CTCAE Grade 3 drug related AE; Any CTCAE Grade 4 drug-related AE; Any subject with drug-related pulmonary complications or thromboembolic complications Determination that the limit of safety and/or tolerability has been reached	Withdraw the subject and Evaluate the risk/benefit profile in other subjects for dose escalations to or above the dose resulting in Grade 3 toxicity and Temporarily or permanently halt study, pending DSMC review, if two subjects develop the same Grade 3 toxicity or if any subject develops a Grade 4 toxicity

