### **7.9 Discontinuation or Temporary Suspension of the Study**

The DSMC or Principal Investigator may terminate this study at any time for safety or administrative reasons. The DSMC or Principal Investigator will terminate the study if the occurrence of AEs or other findings suggests an unacceptable risk to the health of the subjects. The study will be interrupted if two subjects, based on two concurrent assessments, develop the same Grade 3 drug-related adverse event (unless related to disease progression of NPC), or if any subject that develops a Grade 4 adverse event, (unless the AEs are of an accidental nature that could not be reasonably attributable to adrabetadex or related to disease progression of NPC). Following review by the DSMC, the study may be resumed as planned, resumed with subjects at a lower dose or discontinued.

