**Table 2. Adverse Events Associated with NPC1**

Category	Adverse Event
HEENT	Eyes Ptosis Abnormal eye movements (including vertical supranuclear gaze palsy and abnormalities of both vertical and horizontal eye movements) Audиologic Progressive high frequency hearing loss Abnormalities in Auditory Brain Stem Responses
	Oromotor/Speech Dysarthria Dysphagia, choking/gagging on food or saliva Copious secretions/drooling
Respiratory	Aspiration Aspiration pneumonia Sleep apnea
Gastrointestinal/ Genitourinary	Hepatomegaly Elevated liver enzymes Splenomegaly Gastrostomy tube related to dysphasia Bladder/bowel incontinence Diarrhea Constipation
Lymphatic	Enlarged tonsils and adenoids
Hematologic	Epistaxis Thrombocytopenia Decreased serum iron, % saturation (not typically associated with low MCV)
Musculoskeletal/Extremities	Hyperreflexia, clonus Motor impairment Gross motor ataxia, impaired ambulation, balance, coordination, decreased muscular strength, muscle contractures Fine motor ataxia, tremor
Neurological	Seizures Cognitive Impairment: Learning difficulty, long/short term memory loss Sleep Disruptions: Gelastic cataplexy Narcolepsy Sleep schedule inversion Fatigue, daytime sleepiness
Psychiatric/Behavioral	Mood swings, diagnosis of major depressive disorder, bipolar disorder, schizophrenia ADD/ADHD diagnosis (not more common than in general pediatric population)

ADD: attention deficit disorder; ADHD: attention deficit hyperactivity disorder; HEENT: head, eyes, ears, nose, throat; MCV: mean corpuscular volume

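### Two study-halt rules differ for a drug-related event also attributed to NPC progression: Table 1 row D pauses dosing, while 7.9 exempts the event on an attribution that nobody independent need confirm

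*Combined protocol and SAP*

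**What the plan says.** **Causality labels (11.2).** There are two. Related means "A reaction that follows at least a plausible temporal sequence from administration of the study drug". Unrelated opens by requiring that there be no relationship to the drug, then adds that "The reaction can be reasonably explained by the known characteristics of the subject" and their clinical state or other therapy. No sentence says which label prevails when both descriptions fit.

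**Table 1 row D (7.8).** The table's title leaves out respiratory and audiological events. Row D is entered by "Any CTCAE Grade 3 drug related AE; Any CTCAE Grade 4 drug-related AE", among other triggers. Its actions include withdrawing the infant and a temporary or permanent instruction to "halt study, pending DSMC review, if two subjects develop the same Grade 3 toxicity or if any subject develops a Grade 4 toxicity". No exemption for disease progression appears.

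**Section 7.9.** At Grade 3, interruption is required when "two subjects, based on two concurrent assessments, develop the same Grade 3 drug-related adverse event (unless related to disease progression of NPC"). At Grade 4, one affected infant is enough, and the exception reads: "unless the AEs are of an accidental nature that could not be reasonably attributable to adrabetadex or related to disease progression of NPC".

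**Where drug and disease overlap.** Section 7.8 requires withdrawal or dose reduction for "central nervous system (altered level of consciousness, seizures) symptoms during drug infusion or within 2 hours post-infusion". Table 2, the list of NPC1-associated events, includes "Seizures Cognitive Impairment: Learning difficulty, long/short term memory loss" and, separately, elevated liver enzymes.

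**The concern.** For a non-respiratory event, row D and 7.9 are the only count-based rules that pause dosing in infants other than the one affected. The respiratory counts in 11.4.2 do not reach these events. When an event is labelled Related and also put down to NPC, row D says halt and 7.9 says the interruption is not required. No text ranks the two.

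If 7.9 is followed, dosing of other infants continues on a judgement that the disease was responsible, and the protocol asks nobody independent to confirm it. If row D is followed, the study pauses for progression that 7.9 meant to exempt. Only one of these can happen for a given event. The first matters more, because these are infants enrolled at up to 6 months of age and 8.2 says the risks of the intravenous drug are not known.

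**Working it through.** No figure in the plan is at issue, so the main check sets the rules side by side.

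**1. Can one event be both drug-related and NPC progression?** Yes, on the protocol's own wording. The Grade 3 clause of 7.9 starts from events that are already drug-related and then exempts those related to progression. If every NPC-explained event were Unrelated, that exemption would do nothing.

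Liver enzymes are a realistic case. Every infant enters with NPC-related liver disease (5.4.1, criterion 3). In the repeat-dose studies (2.3.1.2), intravenous drug at 400 mg/kg slightly raised ALT in dogs, and slightly raised transaminases remained after recovery in rats.

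**2. What does each rule do with an event attributed to NPC?**

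| Event | Label | Table 1 row D | Section 7.9 |
|---|---|---|---|
| Same Grade 3, two infants | Related | halts | exempt; also needs two concurrent assessments |
| Same Grade 3, two infants | Unrelated | not entered | does not interrupt |
| One Grade 4, natural reading of 7.9 | Related | halts | exempt |
| One Grade 4, natural reading | Unrelated | not entered | exempt |
| One Grade 4, other reading | Related | halts | interrupts |
| One Grade 4, other reading | Unrelated | not entered | interrupts |

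The natural reading gives progression its own exemption at Grade 4. The other reading gives it none. The rules give different answers for a Related event at Grade 3 on any reading, and at Grade 4 on the natural reading. The last row is a difference in scope: 7.9 covers any Grade 4 adverse event and row D only drug-related ones.

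**3. What is exposed if dosing continues?**
- Next dose: the Phase 1 interval is 4 ± 1 days (9.1), so 3 to 5 days. In Phase 2 it is about a month.
- Second assessment at Grade 3: the term is not defined. A same-day repeat adds 0 delay. If it means the next scheduled Phase 1 laboratory draw (an assumption), draws are 2 weeks apart (6.6.1), and 2 weeks × 2 doses per week = 4 doses.
- Infants on dosing at once: about 4 enrolments per year (5.3) × time on dosing. Phase 1 runs 11 intervals × 3 to 5 days = 33 to 55 days, so 4 × 33/365 = 0.36 to 4 × 55/365 = 0.60. If all enter Phase 2, add 30 days to dose 13 and 152 days for five monthly intervals: 215 to 237 days, so 4 × 215/365 = 2.36 to 4 × 237/365 = 2.60.
- First completion-based DSMC review (after two infants complete, 11.4), counted from the second infant's first dose. Phase 1 only: 33 + 5 = 38 to 55 + 9 = 64 days, or 5.4 to 9.1 weeks. If completion includes Phase 2, with its ± 7-day start window: 33 + 23 + 152 + 5 = 213 to 55 + 37 + 152 + 9 = 253 days, or 30 to 36 weeks.

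**4. How often?** The documents give no rate. Suppose each of 12 infants independently has probability p of a qualifying event (an assumption). The chance of at least one Grade 4 event is 1 − (1 − p)^12: 22% at p = 0.02, 46% at 0.05, 72% at 0.10 and 93% at 0.20. For the same Grade 3 event in two or more infants, the exact binomial gives 2%, 12%, 34% and 73%. The spread shows that frequency cannot be pinned down; it is not an estimate.

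**The case against.** The strongest reply is that both rules can be obeyed. The exemption in 7.9 lifts only its own mandatory interruption. It does not forbid a halt, and the DSMC or Principal Investigator may stop the study at any time. Pausing under row D pending DSMC review breaches nothing. This stands, so a reader who infers that the rules cannot both be followed goes too far. What remains is that nothing obliges the investigator to choose the cautious course.

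Second, the Table 1 column heading for safety decisions carries an asterisk whose footnote is not in the available text. It may qualify row D. The statement that row D has no exemption is limited accordingly.

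Third, attribution is not without guidance. Section 11.1 explains what a reasonable possibility of causation means, 11.7.1 requires that assessment for every SAE, 11.4.1 brings the local monitor and DSMC into the tolerability review, and 9.11 gives the DSMC a part in those decisions. The opening of the Unrelated definition also leans towards Related when a drug link is possible. This is fair, but none of it makes the 7.9 exemption depend on anyone's confirmation. The SAE route in 11.7.1 names the Principal Investigator, FDA and IRB, not the DSMC.

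Fourth, other safeguards exist: withdrawal or dose reduction of the affected infant (7.8), row D's own risk/benefit evaluation for escalation in other subjects, DSMC review of all six Cohort 1 infants before Cohort 2 (5.6), and earlier or ad hoc DSMC review (11.4, 11.5). These reduce the risk. They act on one infant, concern escalation, or are discretionary; none pauses current dosing of the others.

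Fifth, the seizure overlap is the weaker illustration. Table 2 serves IRB reporting, not causality, and section 2.1 places neurological disability after early visceral disease. The liver-enzyme overlap does not have the second weakness.

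**Conclusion.** Wrong as written: the two halt rules are inconsistent, with minor to moderate weight. The Grade 3 difference holds on any reading of 7.9. The Grade 4 difference holds on the natural reading and disappears for a Related event on the other. Both assume that the missing Table 1 footnote does not already settle the matter.

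The trigger is small: one infant of about 12 (maximum 15) at Grade 4, or two at Grade 3. The exposure is limited as well. With 0.4 to 0.6 infants on dosing on average if none enters Phase 2, and 2.4 to 2.6 if all do, a missed or unneeded pause touches few infants at a time, plus new enrolment.

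A reader might also infer that an Unrelated Grade 4 event exposes a second contradiction, because on the other reading only 7.9 halts for it. The documents do not support that: a wider rule applying where a narrower one is silent is not a conflict. Nor do they support saying that infants are left unprotected, given the safeguards above. The supported point is narrower. Whether other infants continue to be dosed can rest on an unconfirmed attribution to the disease.

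**What to change.** 1. Keep row D's trigger (the same Grade 3 toxicity in two infants, or any Grade 4) as an immediate temporary pause. Do not redirect row D to 7.9 alone: that would give up its unexempted Grade 4 halt and import the undefined second assessment at Grade 3.
2. In both row D and 7.9, state that the NPC-progression exemption covers both grades and applies only after the DSMC or the independent local monitor confirms it, with dosing paused until then.
3. Do not require a second assessment before the Grade 3 pause.
4. In 11.2, state that an event with plausible timing is Related unless another cause clearly explains it.

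The tie-break narrows the room for choosing a label but does not remove it: a Grade 3 event firmly classed as Unrelated still reaches neither rule.

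The cost is wording in three places and no extra assessments. In operation it means an occasional ad hoc DSMC meeting, which 11.5 already allows, or a local-monitor call, and a short pause. At two doses a week, each week of pause delays or loses about 2 of 12 Phase 1 doses for each infant then in Phase 1. Some pauses will turn out to be for progression alone.
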